4. ECONOMIC SUBSTUDY

This study will include a prospective economic analysis of US sites if contracted by the Sponsor. Please refer to Appendix C for complete description.

5. FUNCTIONAL TESTING

Each subject enrolled in the study will be asked to perform a series of functional tests under static and dynamic conditions that they routinely encounter during their daily lives. These tests include:

1. The Timed “Get-up and Go” Test (TUG) is a functional test that physical therapists have been using since the late 1980s to assess balance in elderly people (Mathias 1985; Podsiadlo 1991; Nordin 2006; Wall 2000). This is a quick test where no special equipment is needed to quantify functional mobility. The test will involve a standard chair, a walkway long enough for a subject to walk 3 meters and turn around, a stopwatch, and an administrator to observe and time the subject. The test administrator will instruct the subject to “go” and start the stopwatch. The subject will rise from the chair, walk 3 meters, turn around, walk back to the chair, and sit down again. Once the subject’s buttocks touch the seat, the stopwatch will be stopped by the test administrator. The subject will be instructed to walk as quickly as they feel safe and comfortable. Assistive devices are allowed only if the subject does not feel safe or cannot do this test without the assistive devices. The test administrator will take note if an assistive device was used during the test. There will be 3 timed trials. The average will be used for data analysis.
2. The 8 Meter Walk is a functional test that measures locomotion. “Locomotion refers to the act of moving from one place to another place, reflecting ambulation ability including walking distance, velocity and quality of gait” (National Institutes of Health 2012). In this test, the distance of 4 meters will be marked by a cone. The subject will begin at one end of the walkway. The test administrator will instruct the subject to “go” and start the stopwatch. The subject will walk towards the cone, around the cone, and back to the starting location at the pace that they normally walk. Once the subject is back at the starting point, the stopwatch will be stopped by the test administrator. There will be 3 timed trials. The average will be used for data analysis.
3. The Timed Up and Down Stairs Test (TUDS) is a functional test that “demands more balance, coordination, strength and muscle control than walking demands” (Lepage 1998; Zaino 2004). This test will involve a stopwatch and a flight of stairs with rails. A usual set of stairs is 12 steps that are 18cm high with a depth of 28cm. The flight of stairs used during testing must have a minimum of 4 steps. The subject will stand at the bottom of the stairs. The test administrator will voice the command “go” and start the stopwatch. The subject will walk as quickly as they feel safe and comfortable to the top of the stairs, turn around, and come back down the stairs. Once the subject is safely back down with both feet back on the landing, the test administrator will stop the stopwatch. The subject may use the rail, but the preference is to do this test without the use of a rail. Assistive devices are allowed only if the subject does not feel safe or cannot do this test without the assistive devices. The test administrator will take note if the rail or an assistive device was used during the test. Again, the subject will be instructed to move as quickly as they

feel safe and are comfortable. There will be 3 timed trials. The average will be used for data analysis.

The Aggregated Locomotor Function (ALF) score is formed by summing the mean of the above three timed tests (McCarthy 2004). Suggested instructions are located in Appendix B.

6. STUDY DURATION

The study subjects will be required to complete follow-up visits at predetermined intervals for 10 years post-implantation. The in-office follow-up visits will occur at 90 days, 180 days, 1 year, 2 years, 5 years, and 10 years post-implantation. The remaining follow-up data collected at years 3, 4, 6, 7, 8, and 9 may be collected via phone call, mail, or email and does not require an in-office visit.

7. STUDY ENDPOINTS

7.1. Primary Endpoints

The primary functional endpoint will be measured by the Aggregated Locomotor Function (ALF) score (TUG, 8 Meter Walk, and TUDS activities) and/or its components at 1 Year post-implantation.

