15. STATISTICAL METHODS

All statistical processing will be performed using SAS® Version 9.3 or later unless otherwise stated.

For continuous variables, descriptive statistics will include n (number of subjects), mean, standard deviation (SD), median, minimum, and maximum. For categorical variables, the number and percentage of subjects in each category will be presented. Appropriate inferential statistics will be used for the primary and secondary efficacy variables.

Populations

The safety population will be comprised of all subjects for whom the procedure is initiated.

The Full Analysis Set (FAS) will be comprised of all subjects for whom the procedure is completed.

The Per-Protocol (PP) population will include all subjects in the FAS who complete the 1 Year visit without significant protocol violations. The PP population will not include subjects who meet any of the following criteria:

- Violated inclusion/exclusion criteria, without sponsor waiver;
- Did not attend the 1 Year visit
- Out of window at the 1 Year visit by +/- 2 months
- Have undergone a procedure to the contralateral knee which may impact the follow-up assessments

Additional criteria may be added to the list to accommodate for unforeseen events that occur during the conduct of the study that impact efficacy assessments. The PP population will be determined prior to data base lock.

Demographic and Baseline Characteristics

Demographic variables (e.g. age, gender, ethnicity, race) and baseline characteristics will be recorded in the CRF. For continuous variables, comparisons between treatment groups will be

conducted with an analysis of variance (ANOVA). A Cochran-Mantel-Haenszel (CMH) test will be used for testing categorical variables.

Efficacy Analysis

Primary Efficacy Analysis

The absolute change from baseline to 1 Year for each primary endpoint will be analyzed using an analysis of covariance (ANCOVA) with factor of treatment (iTTotal CR, OTS) and the respective baseline score as a covariate. The least squares means will be presented along with the observed means.

Secondary Efficacy Analyses

Secondary endpoints will be analyzed as follows:

- The absolute change from baseline to 1 Year for each subscale of KSS will be analyzed using an analysis of covariance (ANCOVA) with factor of treatment (iTTotal CR, OTS) and the respective baseline score as a covariate. The least squares means will be presented along with the observed means.

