- The absolute change from baseline to 1 Year for each subscale of KOOS will be analyzed using an analysis of covariance (ANCOVA) with factor of treatment (iTTotal CR, OTS) and the respective baseline score as a covariate. The least squares means will be presented along with the observed means.
- Post-operative limb alignment will be dichotomized as in and out of “safe zone” (+/- 3 degrees neutral mechanical axis alignment). The proportion of subjects in each study arm summarized and compared using a CMH test.

Safety Analysis

Procedure-related and device-related adverse events (AEs) occurring during the study will be recorded. For the safety population, AEs will be summarized by study arm, the number of subjects reporting AEs, severity, relationship to procedure, relationship to device, and seriousness.

In addition to overall AE summaries, AEs will be summarized for the following study periods:

- Day of procedure to 6 months post procedure
- Annual summaries (1 Year, 2 Year, etc.) from day of procedure

All serious adverse events (SAEs) will be summarized by study arm, severity, relationship to procedure, and relationship to device. SAEs will also be listed by subject.

All information pertaining to AEs noted during the study will be listed by subject.

The Fisher’s Exact test will be used to compare the proportion of subjects in each study arm who have the following:

- procedure-related AEs
- device-related AEs
- revision procedures

Missing Efficacy Data Imputation

The last observation carried forward (LOCF) method will be used to impute missing efficacy data.

Sample Size Determination

A total sample size of a minimum of 450 and a maximum of 600 subjects will be prospectively enrolled in a consecutive fashion, to each arm of the study (approximately 225-300 in the iTotal CR arm and 225-300 in the OTS arm). To ensure that enrollment in each arm remains relatively even, sites assigned odd site numbers will begin by enrolling off-the-shelf subjects and even numbered sites will begin by enrolling ConforMIS subjects. Based on data from a previous study, it is expected that a minimum of 450 and a maximum of 600 total subjects will provide greater than 80% power for the primary functional endpoint.

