4.37 Yards
2.35 Smoot

3. Place the cone on top the piece of the second piece of tape.

Test Instructions:

1. The subject should stand at the first piece of tape.
2. Instruct the subject using the following command:
 - “On the word ‘GO’ you will walk to the cone, walk around the cone, and then walk back towards first piece of tape. Walk as quickly as you feel safe.”
3. Stop watch instructions:
 - Start timing when you say “GO.”
 - Stop timing when the subject’s second foot touches the first piece of tape.
4. There will be 3 individually timed tests.

Timed Up & Down Stairs Test

Equipment needed: Stopwatch, Flight of Stairs

Test Set Up:

1. Count the number of steps and record this on the form. Count the steps in one direction. For example, in the diagram above, there are 5 steps. The flight of stairs used in this test must have a minimum of 4 stairs.
2. If possible, please use the same flight of stairs for all subjects.

Test Instructions:

1. The subject should stand at the bottom of the flight of stairs.
2. Instruct the subject using the following command:
 - “I am going to ask you to stand at the bottom of the stairs so that your first step is up. My commands will be ‘ready, set, GO’. Then you are going to walk as quickly as you feel safe and comfortable to the top of the stairs, turn around, and come back down. You may use the rail, but if you can go without the rail, please try to do so.”
3. Stop watch instructions:
 - Start timing when you say “GO.”
 - Stop timing when the subject’s second foot touches the landing at the bottom of the stairs.
4. At the end of each test, ask the subject about their pain level during the test, their confidence, and their comfort in completing another trial.
5. If the subject answers “no” concerning their comfort in completing the stairs, then do not have them attempt the stairs again.
6. There will be 3 individually timed tests if the subject feels comfortable completing each test.

Time Point (check one):  Pre-op  90 Days  180 Days  Year 1  Year 2  Year 5  Year 10														
Trial	Get Up & Go Time (mm:ss.ms)	Get Up & Go Rest Time (mm:ss.ms)	Arms Used?	Circle Pain Level After Each Trial										
1	_____ : _____ . _____	_____ : _____ . _____	Y N	0	1	2	3	4	5	6	7	8	9	10
2	_____ : _____ . _____	_____ : _____ . _____	Y N	0	1	2	3	4	5	6	7	8	9	10

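### The primary endpoint is ALF and/or its components, with no alpha, testing order or success rule, so any of four overlapping variables could decide the primary claim

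*Combined protocol and SAP*

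**What the plan says.** Section 7.1 (Primary Endpoints) reads: "The primary functional endpoint will be measured by the Aggregated Locomotor Function (ALF) score (TUG, 8 Meter Walk, and TUDS activities) and/or its components", assessed at 1 Year. Section 5 (Functional Testing) defines the composite: "The Aggregated Locomotor Function (ALF) score is formed by summing the mean of the above three timed tests". The four candidates are thus three timed tests and their sum.

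Section 15 (Primary Efficacy Analysis) says: "The absolute change from baseline to 1 Year for each primary endpoint will be analyzed". The model is an ANCOVA with treatment as factor and the matching baseline score as covariate. The only general statement on inference is in the opening of Section 15: "Appropriate inferential statistics will be used for the primary and secondary efficacy variables".

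The sample size paragraph says that 450 to 600 subjects "will provide greater than 80% power for the primary functional endpoint". It refers to a previous study but names no variable, difference, SD or alpha.

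No section gives a significance level, sidedness, formal hypothesis, order of testing, multiplicity adjustment or success rule.

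**The concern.** The and/or wording lets a component stand beside ALF or in its place, and nothing elsewhere settles which. Three readings fit the text:

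- ALF decides and the components are supportive.
- Any one of the four is enough.
- All four must succeed.

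These have different error rates and different power. The plan does not say that one success out of four is sufficient, but it permits that reading, and it permits the choice to be made after the results are known. A positive TUG or stair result with a null ALF could be presented as the primary finding with no protocol deviation. The power statement has the same problem: it cannot be matched to a defined test.

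**Working it through.** **The plan's own figure.** Power above 80% cannot be reproduced, because the variable, difference, SD, alpha and sidedness are all missing. It can only be inverted. Assume two-sided 0.05, equal arms, complete data and no gain from the baseline covariate. The smallest standardised difference with 80% power is

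d = (z(1−α/2) + z(0.80)) × √(2/n)

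- 225 per arm: (1.960 + 0.842) × √(2/225) = 2.802 × 0.0943 = 0.264 SD
- 300 per arm: 2.802 × √(2/300) = 2.802 × 0.0816 = 0.229 SD

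Whether the previous study supports differences of that size, and for which of the four variables, cannot be seen.

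**Error rate if any one of the four may carry the claim.**

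From the documents: ALF is the sum of the three component means (Section 5), and each variable gets its own ANCOVA (Section 15).

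Assumed: each test is two-sided at 5%, there is no true difference, and the three component test statistics share a common correlation ρ. The documents give no value for ρ, so a range is shown.

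With equal component SDs, the ALF statistic is

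Z(ALF) = (Z1 + Z2 + Z3) / √(3 + 6ρ)

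and its correlation with each component is √((1 + 2ρ)/3): 0.58 at ρ = 0, 0.82 at ρ = 0.5 and 0.97 at ρ = 0.9. Four independent tests would give 1 − 0.95⁴ = 18.5%, which is too high here because ALF is built from the other three. Simulation with at least 1,000,000 draws per setting gives, to within about 0.1 percentage point:

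| ρ | Any of four, either direction | Any of the three components | Component significant, ALF not | Any of four, one named direction |
|---|---|---|---|---|
| 0 | 16.1% | 14.3% | 11.1% | 8.2% |
| 0.3 | 14.5% | 13.6% | 9.5% | 7.2% |
| 0.5 | 12.9% | 12.5% | 8.0% | 6.5% |
| 0.7 | 11.1% | 10.9% | 6.0% | 5.5% |
| 0.8 | 9.9% | 9.8% | 4.9% | 4.9% |
| 0.9 | 8.4% | 8.4% | 3.4% | 4.2% |

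The ρ = 0 row for the components agrees with 1 − 0.95³ = 14.3%. At ρ = 0.95 the any-of-four rate is still about 7%. Making one component's SD two or four times the others changes the any-of-four rate very little for ρ of 0.5 or more; at ρ = 0 it becomes 15.9% and 15.3%.

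The nominal rate is 5% for the either-direction columns and 2.5% for the last column. Nearly all the excess comes from the three components; adding ALF to them contributes little.

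**Cost of controlling the error across all four.** Holm's first step is 0.05/4 = 0.0125, with z = 2.498:

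- 225 per arm: (2.498 + 0.842) × 0.0943 = 0.315 SD
- 300 per arm: (2.498 + 0.842) × 0.0816 = 0.273 SD

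For one variable at the 0.264 SD difference, power at 0.0125 is Φ(2.802 − 2.498) = 62%. Restoring 80% takes about 320 per arm instead of 226. This is the worst case, because Holm relaxes after the first rejection and the four variables are correlated.

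**The case against.** Section 7.1 speaks of one endpoint and names ALF first, and the sample size paragraph repeats the singular. ALF as lead variable with supportive components is a plausible intent. The plural in the heading of Section 7.1 and the word each in Section 15 may be left over: the protocol history shows patient-reported outcomes removed as a primary endpoint in version 5.0. If all four had to succeed, type I error would not be inflated at all. This is fair as to intent, and the finding does not rest on the plural. But the and/or phrase in the current text allows a component to replace ALF, and no other sentence closes that door.

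The either-direction rates also count findings against the iTotal CR, and mixed directions across components. For a superiority claim in one direction, the last column of the table is the relevant one, and a component winning without ALF falls to about 4.0%, 3.0% and 1.7% at ρ = 0.5, 0.7 and 0.9. The absolute figures are about half, but so is the nominal rate, and the relative inflation is similar. Since the stated objective is only to compare the groups, neither version is wrong.

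Three timed mobility tests on one subject at one visit could be strongly correlated, which would favour the lower end of the range. No value is given, and the rate stays above nominal even at 0.95. The 16.1% figure is a ceiling only among equal, non-negative correlations.

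Finally, allocation is not randomised, so control of multiplicity alone would not make a positive result reliable. That is true, but it is a separate matter.

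**Conclusion.** The concern holds. The primary variable and the decision rule are undefined, and following the plan as written leaves the error rate of the primary claim uncontrolled.

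If any one of four tests at two-sided 5% may carry the claim, the false-positive rate is roughly 8% to 14% for component correlations from 0.9 down to 0.3, or about 4% to 7% in one named direction against 2.5%. Those sizes rest on the assumed alpha, the any-one-counts rule and the assumed correlations. The ambiguity itself rests on the text alone. It should be fixed before the primary analysis, since it decides what the study may claim.

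**What to change.** - **Section 7.1:** define the primary endpoint as the change from baseline to 1 Year in total ALF score, and delete the reference to components.
- **Section 15, primary analysis:** refer to a single primary endpoint and state alpha and sidedness, for example two-sided 0.05. Make TUG, 8 Meter Walk and TUDS secondary: either tested only if ALF is significant, with Holm within the three, or reported descriptively.
- **Sample size paragraph:** tie the power statement to ALF and give the assumed difference, SD and alpha from the previous study.
- **Missing components:** say how ALF is formed when a test is absent or incomplete. Appendix B lets subjects decline further stair trials, and last observation carried forward cannot supply a missing baseline.
- **Timing:** date the change before any comparative 1 Year results are seen. Section 13 allows the sponsor to review patient outcomes periodically, so a later choice would not protect the error rate.

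If the sponsor wants a component to be able to carry the claim, pre-specify Holm over all four at an overall 0.05 and accept the higher detectable difference (0.264 to 0.315 SD at 225 per arm; 0.229 to 0.273 SD at 300).

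The recommended version needs no extra patients or data. Its price is that a component alone can no longer support the primary claim. A sole ALF primary also leans on its parts being measured alike, so two points need reconciling. Section 5 asks for the subject's usual pace on the 8 Meter Walk, while Appendix B asks for the fastest pace the subject feels is safe. For the stairs, the minimum is 4 steps and Appendix B says only: "If possible, please use the same flight of stairs for all subjects".

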7.2. Secondary Endpoints

The study secondary endpoints are:

1. The 2011 Knee Society Knee Scoring System[®] (KSS) and/or its subscales at 1 Year post-implantation
2. The Knee Injury and Osteoarthritis Outcome Score (KOOS)
3. Incidence of major procedure-related and device-related complications, including revision rates
4. Post-operative limb alignment

8. INCLUSION AND EXCLUSION CRITERIA

Per CONSORT data reporting guidelines, all patients considered for this study will be tracked on a log documenting their eligibility, and enrollment status. For further details, please refer to Appendix D.

8.1. Inclusion Criteria

1. Clinical condition included in the approved Indications For Use for the iTotal CR
2. Osteoarthritis, as confirmed by the investigator's assessment of disease status at screening visit that warrants a TKR procedure. Disease status is determined by Clinical and Radiographic assessment
3. Willingness to participate in the clinical study, to give informed consent and to attend all follow-up visits
4. > 18 years of age

8.2. Exclusion Criteria

1. Subject will require a simultaneous bilateral procedure

2. Lower extremity surgery (orthopaedic or ligament injury) on either limb to the hip, ankle, feet occurring or expected to occur within 1 year of surgery on the evaluated knee
3. Severe ($> 15^\circ$) fixed valgus or varus deformity
4. Severe ($> 15^\circ$) extension deficit
5. Severe instability due to advanced loss of osteochondral structure
6. Loss of bone or musculature, osteoporosis, neuromuscular or vascular compromise in the area of the joint to be operated on to an extent that the procedure is unjustified
7. Insufficient bone stock on the femoral or tibial surfaces
8. Contralateral knee replacement occurring or expected to occur within 6 months of surgery on the evaluated knee
9. BMI > 40
10. Active malignancy (defined as a history of any invasive malignancy – except non-melanoma skin cancer), unless patient has been treated with curative intent and there have been no clinical signs or symptoms of the malignancy for at least 5 years
11. Poorly controlled diabetes (defined as HbA1c > 7 or surgeon discretion)
12. Immunocompromised
13. Other physical disability affecting the hips, spine, or contralateral knee that limits function
14. Disabling chronic pain with narcotic dependence
15. Compromised PCL or collateral ligament
16. Prior history of failed implant surgery of the joint to be treated, including Unicompartmental Knee Arthroplasty (UKA), or Bicompartmental Knee Arthroplasty (BKA)
17. Prior history of failed High Tibial Osteotomy (HTO)
18. Participation in another clinical study which would confound results
19. Inability to complete the protocol in the opinion of the clinical staff due to safety or other reasons

9. SITE SELECTION

All sites will be selected by a Site Selection Committee based on a set of defined criteria. The Site Selection Committee will be led by Clinical Affairs. The site selection criteria includes but is not limited to:

- Interest in participating in the study as demonstrated by responsiveness
- Demonstrated technical and surgical skills with iTotal CR device - Investigator must have completed a cadaver training at minimum prior to enrolling their first subject
- Sufficient patient volume to expect timely subject enrollment
- Ability to adhere to the standards of Good Clinical Practice (GCP) and Good Documentation Practice (GDP)
- Clinical study experience and resources that demonstrate good compliance with study requirements and timely, complete documentation of subject follow-up
- Willingness to allow personnel from ConforMIS (or its designate) access to the hospital records, Investigator's study records, data and patient files as they pertain to the study

During the study, an oversight committee comprised of three individuals: the Lead Study Principle Investigator in the U.S., a second study investigator, and a statistician will review site

performance and data integrity. This committee will determine if the data collected is consistent with the cohort, and meets the minimum enrollment threshold for the study.

If a site has not enrolled a minimum of 20 subjects into the study, data may be excluded from analysis. Likewise, if data quality is inadequate or data is incomplete, the committee may exclude a site's data.

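### Section 9 makes dropping a site's data optional, on partly undefined grounds, with no pre-lock deadline or blinding to results, and conflicts with the Section 15 populations

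*Combined protocol and SAP*

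**What the plan says.** Section 9 (Site Selection) sets up an oversight committee of three: "the Lead Study Principle Investigator in the U.S., a second study investigator, and a statistician". It reviews site performance and data integrity while the study runs. Two rules follow.

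- **Size.** "If a site has not enrolled a minimum of 20 subjects into the study, data may be excluded from analysis". The number is fixed in advance but its use is optional. The sentence does not say who decides, although the preceding paragraph gives the enrolment-threshold check to the committee.
- **Quality.** "Likewise, if data quality is inadequate or data is incomplete, the committee may exclude" a site's data. This is also optional, and no threshold or definition is given.

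Section 15 (Statistical Methods, Populations) says: "The Full Analysis Set (FAS) will be comprised of all subjects for whom the procedure is completed". It also says: "The safety population will be comprised of all subjects for whom the procedure is initiated". Neither definition makes an exception for an excluded site. For the per-protocol (PP) set, further exclusion criteria may be added: "Additional criteria may be added to the list to accommodate for unforeseen events that occur during the conduct of the study". That set has a deadline: "The PP population will be determined prior to data base lock".

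Section 3 (Study Design) blinds the person who runs the functional tests. It also asks investigators and study staff to try to preserve the blind by restricting access to data and films.

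**The concern.** A rule that lets someone leave out a whole site is safe if its trigger is objective, if it is applied before results are known, or if it cannot affect the main result. Section 9 secures none of these. The size trigger is objective but may be used for one small site and not for another. The quality trigger has no criterion. Follow-up lasts 10 years (Section 6) and the primary endpoint is at 1 year (Section 7.1), so a decision taken while the study runs could come after the primary data exist.

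Allocation is by alternating series of 10, not by randomisation (Section 3), so the comparison is already open to questions about selection. If a site were dropped, readers could not tell whether the result had influenced the decision. They also could not tell which analyses the exclusion applied to.

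**Working it through.** **1. The text, side by side.**

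| Question | Section 9, site exclusion | Nearest text elsewhere |
|---|---|---|
| Criterion | Under 20 subjects (optional); inadequate or incomplete data (undefined) | None |
| Deadline | None; review takes place during the study | Section 15 sets a pre-lock rule, for the PP set only |
| Blind to outcome by arm | Not stated | Section 3: best-effort wording that does not mention the committee or this decision |
| Population affected | Analysis in general | Section 15: full analysis set is all completed procedures, safety population all initiated ones |

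The last row is a direct conflict. If a site is excluded under Section 9, its subjects with completed procedures still meet the definition of the full analysis set, and those with initiated procedures still meet the definition of the safety population.

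**2. Scale, as an illustration.** The plan gives no figure to reproduce here: Section 15 states no alpha, effect size or SD.

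Assumptions: two-sided 5% (critical value 1.96); 20 equal sites, the maximum in Section 3 (450/20 = 22.5 subjects each); equal arms within each site; no true difference; no site effects; and a chooser who sees results by arm and drops the sites least favourable to one given arm.

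Let D_j be the standardised arm difference at site j, standard normal under the null, with D(1) the smallest and D(2) the next.

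- No choice: z = ΣD_j/√20, and P(z > 1.96) = 2.5%.
- One site dropped: z = (ΣD_j − D(1))/√19. For 20 standard normals the mean of D(1) is −1.87 and its variance 0.276, and its covariance with the sum is 1. So z has mean 1.87/√19 = 0.43 and variance (20 + 0.276 − 2)/19 = 0.962, SD 0.981. A normal approximation gives 1 − Φ((1.96 − 0.43)/0.981) = 1 − Φ(1.56) ≈ 5.9%. Simulation of at most one site dropped: 5.9%.
- Two sites dropped: D(2) has mean −1.41, and D(1) + D(2) has variance 0.705 and covariance 2 with the sum. The mean is (1.87 + 1.41)/√18 = 0.77 and the variance (20 + 0.705 − 4)/18 = 0.928, SD 0.963. The tail is 1 − Φ((1.96 − 0.77)/0.963) ≈ 10.9%. Simulation of at most two: 10.9%.

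These are chances of a false result favouring the chosen arm, so the baseline is 2.5%, not 5%. Counting false results in either direction, dropping the one least favourable site gives about 6.7% against 5%.

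**3. Sensitivity to site differences.** At most one of 20 sites dropped, same one-sided measure, analysis without a site term (as in the Section 15 ANCOVA). In both rows half the sites lean to each arm.

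| Site split | Between-site SD (in residual SDs) | No choice | Option to drop one |
|---|---|---|---|
| 12.5/10 (N = 450) | 0 / 0.3 / 0.5 | 2.4% / 2.1% / 1.7% | 5.9% / 5.2% / 4.3% |
| 20/10 (N = 600) | 0 / 0.3 / 0.5 | 2.5% / 3.7% / 5.2% | 6.0% / 8.3% / 11.3% |

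The level moves down with near-balanced sites and up with unbalanced ones. In each case the option to drop one site multiplies the no-choice rate by a little over two.

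**The case against.** The best case for the plan runs as follows. Oversight by investigators with a statistician is ordinary practice. The size threshold is a prespecified number. Section 3 tells investigators and staff to protect the blind by limiting access to data, and Section 15 fixes the PP set before lock. Every rate above needs a chooser who sees results by arm and acts on them, and the documents do not say that the committee sees them.

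Much of this stands. The committee's composition is not an error in itself, and the rates describe what the wording permits, not what is expected. But the Section 3 sentence is best-effort and does not reach this decision. Investigators also implant the device (Section 11.2), so they know the arm of subjects they operate on. The PP deadline is not linked to Section 9.

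Some stronger readings are tempting but unsupported:

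- **That the committee learns outcomes from the sponsor's periodic data review (Section 13).** Nothing connects the two; silence is not evidence of a link.
- **That there is a third ground for exclusion.** Section 9 does say "This committee will determine if the data collected is consistent with the cohort", but it lists only size and data quality as reasons to exclude.
- **That adverse events and revisions from a dropped site will be lost.** Section 15 summarises adverse events on the safety population, which has no site exception. The conflict needs resolving, but planned loss of safety data does not follow.
- **That dropping a small, unbalanced site would by itself distort the estimate.** For a 10/5 site whose level is 1 SD off, the shift is about (10 − 5)/225 = 0.02 SD, against a standard error of 2/√450 = 0.09 SD.
- **That the 11.3% in the last table measures the effect of exclusion.** In that setting 5.2% arises with no exclusion at all, from ignoring site differences.

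**Conclusion.** The point holds as a gap in the wording and an inconsistency between Sections 9 and 15. Site exclusion is optional. Its quality ground is undefined, and neither ground has a pre-lock deadline or stated blinding to outcome by arm. The rule names no population and does not fit the definitions of the full analysis set and the safety population. No other section cures this.

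The possible size is moderate: from 2.5% to about 6% with one site and about 11% with two. This rests on 20 equal sites, no site effects, an assumed two-sided 5% level and a fully informed chooser. The rates vary up or down with between-site differences and site balance. A reader might infer that results-driven exclusion is intended, but nothing in the documents suggests it. The change is worth making because it is cheap and removes the question.

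**What to change.** Amend Sections 9 and 15 as follows.

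1. State that the main efficacy analysis includes eligible subjects from all sites, whatever the site's size.
2. State that the safety analysis always uses the full safety population from all sites.
3. Show results without small or poor-quality sites only as sensitivity analyses.
4. If exclusion for documented data-integrity failure is kept, write the criteria down. Have them applied by people who have no access to outcome data and are not involved at that site. Record each decision, with its reason, before database lock.

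The cost is a few sentences in the protocol and SAP. The downside is that some noisier data stay in the main analysis.
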